#### 7.2.2.1. Treatment-Emergent Laboratory Abnormalities

Treatment-emergent laboratory abnormalities are defined as values that increase at least 1 toxicity grade from baseline at any postbaseline time point, up to and including the date of last dose of study drug plus 30 days for subjects who permanently discontinued study drug. If the relevant baseline laboratory value is missing, then any abnormality of at least Grade 1 will be considered treatment emergent.

#### 7.2.2.2. Summaries of Laboratory Abnormalities

Laboratory data that are categorical will be summarized using the number and percentage of subjects in the study with the given response at baseline and each scheduled postbaseline visit.

The following summaries (number and percentage of subjects) for treatment-emergent laboratory abnormalities will be provided by analyte in each age group; subjects will be categorized according to the most severe postbaseline abnormality grade for a given analyte:

- Graded laboratory abnormalities
- Grade 3 or above laboratory abnormalities

For all summaries of laboratory abnormalities, the denominator is the number of subjects with nonmissing postbaseline values up to 30 days after last dose for the laboratory parameter of interest.

A by-subject listing of treatment-emergent Grade 3 or above laboratory abnormalities will be provided by subject ID number and visit in chronological order. This listing will include all test results that were collected throughout the study for the analyte of interest, with all applicable severity grades or abnormal flags displayed.

For subjects with at least one event of treatment-emergent Grade 3 or above laboratory abnormality of creatine kinase (CK) or lipase, a listing of AEs will be provided.

#### 7.2.2.3. On-Treatment Liver-Related Laboratory Events

The following liver-related laboratory events will be summarized for each age group using data from all the on-treatment postbaseline visits (up to 3 days after the last dose of any study drug):

- AST or ALT  $> 3 \times$  ULN and total bilirubin  $> 2 \times$  ULN
- ALT  $> 5 \times$  ULN
- Total bilirubin  $> 2 \times$  ULN

For the composite criterion of AST or ALT and total bilirubin, AST or ALT and total bilirubin must meet the specified cut-offs at a given postbaseline time point; subjects will be counted once when the criterion is met. The denominator will be the number of subjects in the Safety Analysis Set with at least 1 postbaseline value of AST or ALT and total bilirubin at the same time point. For individual laboratory tests, subjects will be counted once based on the most severe postbaseline values when the criterion is met. The denominator will be the number of subjects in the Safety Analysis Set with at least 1 nonmissing postbaseline value for the test. A listing will be provided including ALT, AST, total bilirubin, direct bilirubin, alkaline phosphatase, HCV RNA ( $\log_{10}$ ) and yes/no flag for subjects meeting at least 1 of the 3 criteria. All the available data for the subjects will be listed.

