4.3. Exclusion Criteria

Subjects who meet *any* of the following exclusion criteria are not to be enrolled in this study.

- 1) Prior use of an HCV NS5A inhibitor
- 2) Current or prior history of clinical hepatic decompensation (eg, ascites, jaundice, encephalopathy, variceal hemorrhage)
- 3) Any of the following laboratory parameters at screening:
 - a) $\text{INR} > 1.2 \times \text{ULN}$
 - b) $\text{Platelets} < 50,000/\text{mm}^3$
 - c) $\text{albumin} < 3.5 \text{ g/dL}$
 - d) $\text{ALT} > 10 \times \text{the upper limit of normal (ULN)}$
 - e) $\text{AST} > 10 \times \text{ULN}$
 - f) $\text{Direct bilirubin} > 1.5 \times \text{ULN}$
 - g) $\text{Estimated glomerular filtration rate} < 90 \text{ mL/min/1.73m}^2$, as calculated by the Schwartz Formula
- 4) Chronic liver disease of a non-HCV etiology (eg, hemochromatosis, Wilson's disease, alpha-1 antitrypsin deficiency)
- 5) Evidence of hepatocellular carcinoma (HCC) or other malignancy (with the exception of certain resolved skin cancers)
- 6) Co-infection with HIV, acute HAV, or HBV (Hepatitis B Surface Ag positive at screening)
- 7) Current or prior history of any of the following:
 - a) Significant cardiovascular, pulmonary, or neurological disease
 - b) Evidence of a gastrointestinal malabsorption syndrome that may interfere with absorption of orally administered medications
 - c) History of solid organ or bone marrow transplantation
 - d) Psychiatric hospitalization, suicide attempt, and/or a period of disability as a result of their psychiatric illness within the last 5 years. Subjects with psychiatric illness (without the prior mentioned conditions) that is well-controlled on a stable treatment regimen for at least 6 months prior to enrollment or has not required medication in the last 12 months may be included.

- 8) Clinically-relevant alcohol or drug abuse within 12 months of screening. A positive drug screen will exclude subjects unless it can be explained by a prescribed medication; the diagnosis and prescription must be approved by the investigator
- 9) Sexually-active males or females of childbearing potential who are not willing to use an effective method of contraception during the study
- 10) Use of any prohibited concomitant medications as described in Section 5.3.
- 11) Investigational agents taken within the past 28 days (except with the express approval of the Sponsor)
- 12) Known hypersensitivity to the study drug, the metabolites, or formulation excipients

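### The on-treatment liver-event table (SAP 7.2.2.3) does not separate elevations carried over from entry from new ones, and no table counts an AST/ALT-plus-bilirubin event first met at the posttreatment Week 4 draw

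*SAP*

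**What the plan says.** SAP 7.2.2.3 defines three liver-related laboratory events: AST or ALT above 3 x ULN together with total bilirubin above 2 x ULN at the same time point; ALT above 5 x ULN; and total bilirubin above 2 x ULN. These "will be summarized for each age group using data from all the on-treatment postbaseline visits (up to 3 days after the last dose". For the two single-test criteria the rule is: "For individual laboratory tests, subjects will be counted once based on the most severe postbaseline values when the criterion is met". The section has no baseline condition, baseline column or shift. It adds a listing with all available data for subjects who meet at least one criterion.

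Protocol 4.3 (exclusion 3) excludes ALT or AST at screening only above 10 x ULN. For bilirubin it limits only the direct fraction, at 1.5 x ULN.

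The neighbouring section, SAP 7.2.2.1, defines treatment-emergent abnormalities as "values that increase at least 1 toxicity grade from baseline at any postbaseline time point", through last dose + 30 days. SAP 7.2.2.2 tabulates these by analyte.

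**The concern.** Safety and tolerability are the primary objective of the Treatment Phase, and there is no control arm to show how many liver-event counts reflect the infection itself. The plan expects raised transaminases at entry. Protocol 1.1 notes that many perinatally infected children have abnormal ALT or AST, and the SAP defines both a baseline-ALT subgroup and an ALT-normalization endpoint.

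A table that ignores baseline therefore mixes two kinds of subject: those whose liver tests rose on treatment and those who came in high and had not yet fallen below the cut-off. With about 100 subjects per age group and events likely to be few, a small carried-over number could change how the row reads.

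The second gap concerns the composite. It is the only criterion in the SAP that looks at transaminase and bilirubin together, and it is not applied to the posttreatment draw.

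**Working it through.** The plan states no figure on this point, so there is nothing to reproduce. The check sets the definitions side by side, counts days, and illustrates the possible size.

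**1. Cut-offs against entry limits**

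| Criterion in SAP 7.2.2.3 | Entry limit in Protocol 4.3 | Can a subject enter already above it? |
|---|---|---|
| ALT > 5 x ULN | ALT ≤ 10 x ULN | Yes, from > 5 to 10 x ULN |
| Total bilirubin > 2 x ULN | None on total bilirubin (direct ≤ 1.5 x ULN) | Yes |
| AST or ALT > 3 x ULN with total bilirubin > 2 x ULN | AST and ALT ≤ 10 x ULN; none on total bilirubin | Yes |

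**2. One child, two tables.** Take a child at 9 x ULN at baseline and 6 x ULN at Week 1. Protocol Appendix 3 grades ALT > 5 to 10 x ULN as Grade 3 and > 10 x ULN as Grade 4.
- SAP 7.2.2.3: 6 > 5, so the child is counted as an on-treatment liver event.
- SAP 7.2.2.1: Grade 3 to Grade 3 is no increase, so the child is not treatment-emergent and would become so only above 10 x ULN.

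**3. Posttreatment draw against the windows.** Chemistry after treatment is scheduled once, at posttreatment Week 4 (Protocol synopsis and Appendix Table 3), with a window of ± 5 days (Protocol 6.5.1). The nominal day is 28 (SAP Table 3-2).
- Permitted days: 28 − 5 = 23 to 28 + 5 = 33, which is 11 days.
- Within last dose + 3 days: 0 of 11.
- Within last dose + 30 days: days 23 to 30, 8 of 11. Days 31 to 33 stay outside.

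**4. Where a composite first met at that draw would appear.** Take ALT at 4 x ULN and total bilirubin at 2.2 x ULN. In Appendix 3, ALT > 2.5 to 5 x ULN and bilirubin > 1.5 to 2.5 x ULN are both Grade 2.
- SAP 7.2.2.3 table: no, because the draw is after last dose + 3 days.
- SAP 7.2.2.2 graded tables, if drawn by day 30: yes, as two separate per-analyte entries where each is a grade increase, with nothing linking them to one subject.
- Grade 3 or above table and listing: not triggered, because neither value is Grade 3.
- General laboratory listing (SAP 7.2): yes, as flagged values.

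**5. Illustrative size of the baseline overlap.** The documents give no baseline ALT distribution, so both rates below are assumptions. Let b be the share entering with ALT > 5 x ULN, r the share of these still above it at a postbaseline visit, and n = 100 the planned age-group size.

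Expected carried-over subjects = n × b × r. Chance of at least one = 1 − (1 − b × r)^n.

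| b | r | Expected | Chance of at least one |
|---|---|---|---|
| 1% | 10% | 100 × 0.001 = 0.1 | 9.5% |
| 1% | 100% | 100 × 0.01 = 1.0 | 63.4% |
| 3% | 50% | 100 × 0.015 = 1.5 | 77.9% |
| 5% | 50% | 100 × 0.025 = 2.5 | 92.0% |
| 5% | 100% | 100 × 0.05 = 5.0 | 99.4% |

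**The case against.** The strongest defence is that the table does what its title says. It reports on-treatment events, not treatment-emergent or drug-related ones, and the 3-day limit is SAP 3.7.2's own definition of on-treatment laboratory data. That stands: the window is a deliberate and consistent choice, and a child at 6 x ULN at Week 1 meets the stated definition.

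The defence can also point to baseline-adjusted hepatic results elsewhere. Graded ALT, AST and bilirubin shifts run to last dose + 30 days. SAP 7.2.1 gives change from baseline by visit, including the posttreatment Week 4 window. ALT normalization shows improvement directly, and the 7.2.2.3 listing lets a reader find the baseline of each flagged subject. All of this stands, but none of it separates the counts in the table or links the two components of a posttreatment composite.

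A reader might infer three stronger points that the documents do not support:
- **Every other laboratory table requires worsening from baseline.** It does not. SAP 7.2.1 counts hemoglobin below 10 and 8.5 g/dL at any postbaseline visit without a baseline condition, and its by-visit summaries include everyone with data. The contrast is with the treatment-emergent graded tables only.
- **Every elevation at entry is counted.** Only those still above the cut-off at an on-treatment postbaseline visit are.
- **The posttreatment month is left out of the hepatic analysis.** Single-analyte rises to last dose + 30 days are captured. What is missing is the composite.

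**Conclusion.** The point holds as a limited gap in a descriptive safety table. The counts in SAP 7.2.2.3 combine elevations persisting from entry with new ones, and a composite first met at the posttreatment Week 4 draw is counted in no table. The definitions and day counts follow from the documents alone.

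The size does not. The range of about 0.1 to 5 carried-over subjects per 100 rests wholly on the assumed 1% to 5% entering above 5 x ULN and 10% to 100% of these persisting, so the effect could be negligible. The documents give no rate for posttreatment composite events either. No estimate, test or efficacy conclusion changes. The point is a worthwhile improvement, not a flaw in the primary safety analysis.

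**What to change.** Keep the on-treatment rows of SAP 7.2.2.3 as they are, and make two additions:

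1. Split each of the three criteria by whether it was already met at baseline, and label only subjects who did not meet it at baseline as emergent. For the composite, met at baseline should mean that both components were above their cut-offs.
2. Add a row for the composite through last dose + 30 days, with the same baseline split. This is the SAP's existing limit for laboratory summaries. It covers Week 4 posttreatment draws on days 23 to 30 but still leaves out those on days 31 to 33, which a footnote should say.

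The cost is a few programmed table rows. All the data are already collected, and no visit, sample or analysis set changes.

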### **7.3. Vital Signs**

Vital signs (systolic and diastolic blood pressure [mmHg], pulse [beats/min]) at each visit, and change from baseline at each visit will be summarized for the Safety Analysis Set in each age group using descriptive statistics (n, mean, SD, median, Q1, Q3, minimum, and maximum). The baseline value will be defined as the last available value collected on or prior to the date/time of first dose of study drug. Change from baseline to a postbaseline visit will be defined as the postbaseline value minus the baseline value.

In the case of multiple values in an analysis window, data will be selected for analysis as described in Section 3.7.3 (Selection of Data in the Event of Multiple Records in a Window). No inferential statistics will be generated.

A by-subject listing of vital signs (systolic and diastolic blood pressure [mmHg], pulse [beats/min], respiration [breaths/min], and body temperature [ $^{\circ}$ C]) will be provided by subject ID number and visit in chronological order.

### **7.4. Body Weight, Height and BMI**

An age- and sex-specific percentile will be derived for each weight, height and BMI measurement according to the downloadable SAS program available on the Centers for Disease Control (CDC) website using the year 2000 growth charts. Methods and SAS program published on the following CDC website will be applied to calculate the percentile {Centers for Disease Control and Prevention (CDC) 2016a, Centers for Disease Control and Prevention (CDC) 2016b}.

Body weight, height, BMI and percentiles for body weight, height, BMI at each visit, and change from baseline at each visit will be summarized for the Safety Analysis Set in each age group using descriptive statistics (n, mean, SD, median, Q1, Q3, minimum, and maximum).

In the case of multiple values in an analysis window, data will be selected for analysis as described in Section 3.7.3 (Selection of Data in the Event of Multiple Records in a Window). No inferential statistics will be generated.

A by-subject listing of body weight, weight percentile, height, height percentile, BMI and BMI percentile will be provided by subject ID number and visit in chronological order.

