2. OBJECTIVES

The primary objective of the PK Lead-in phase is:

- To evaluate the steady state pharmacokinetics (PK) and confirm the dose of sofosbuvir/velpatasvir (SOF/VEL FDC) in pediatric subjects with chronic hepatitis C virus (HCV) infection

The primary objective of the Treatment Phase of this study is:

- To evaluate the safety and tolerability of SOF/VEL FDC for 12 weeks in pediatric subjects with chronic HCV

[figure not shown]
The secondary objective of the PK Lead-in Phase is:

- To evaluate the safety, tolerability, and antiviral activity of 7 days of dosing of SOF/VEL FDC in pediatric subjects with chronic HCV

The secondary objectives of the Treatment Phase of this study are:

- To determine the efficacy of SOF/VEL FDC for 12 weeks in pediatric subjects with chronic HCV infection, as assessed by the proportion of subjects with sustained virological response (SVR) 12 weeks after cessation of treatment (SVR12)
- To determine the proportion of subjects with SVR 4 and 24 weeks after cessation of treatment (SVR4 and SVR24)
- To evaluate the proportion of subjects with virologic failure, including breakthrough/nonresponse and relapse
- To evaluate the kinetics of circulating HCV RNA during treatment and after cessation of treatment
- To evaluate the emergence of viral resistance to SOF and VEL during treatment and after cessation of treatment
- To evaluate the effect of treatment with SOF/VEL FDC on quality of life as measured by PedsQL™ Pediatric Quality of Life survey
- To evaluate the effect of SOF/VEL FDC on growth and development of pediatric subjects during and after treatment
- To evaluate the acceptability, including palatability, of formulations used in the study

The exploratory objective of this study is:

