3. STUDY DESIGN

3.1. Endpoints

The appropriateness of the SOF/VEL FDC dose will be assessed by evaluating the steady-state PK of the VEL, SOF, and GS-331007 at Day 7 (C_{max} , T_{max} , C_{last} , T_{last} , C_{tau} , AUC_{tau} and $t_{1/2}$). The primary endpoint of the PK Lead-in Phase is to determine steady-state PK, is AUC_{tau} of VEL, SOF, and its major metabolite (GS-331007).

The primary endpoint of the Treatment Phase is assessment of any AEs with a focus on AEs that lead to discontinuation of study drug.

The secondary endpoints of the PK Lead-in Phase are:

- Antiviral activity measurements, including assessment of HCV RNA from baseline through Day 7.
- Any AE leading to permanent discontinuation of study drug.

The secondary endpoints of the Treatment Phase are:

- The proportion of subjects with sustained virological response (SVR) 12 weeks after cessation of treatment (SVR12). SVR12 is the key efficacy endpoint.
- The proportion of subjects with HCV RNA < LLOQ at 4 or 24 weeks after cessation of treatment (SVR4 and SVR24).
- The proportion of subjects with virologic failure, including breakthrough/nonresponse and relapse
- The proportion of subjects with HCV RNA < LLOQ on treatment
- Emergence of viral resistance to SOF and /or VEL during treatment and treatment is discontinued
- HCV RNA change from Day 1
- Quality of life endpoints and neuropsychiatric assessments as measured by PedsQL™ Pediatric Quality of Life survey
- Growth and development measurements including height and weight percentiles, Tanner Stage, parental height, and bone age
- Acceptability assessed by swallowability and palatability

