6.10.5. Height & Weight Measurement

Height and weight measurement will be collected at each study visit. The difference in body weight and height measurements between Day 1 and End of Treatment, posttreatment Week 12, and posttreatment Week 24 will be calculated. Parental heights will be recorded at Screening or Day 1, unless unknown (eg, subject adopted, biological parent(s) deceased, etc).

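### The only age- and sex-standardised growth change in SAP 7.4 is in CDC percentile points, which are not an interval scale and understate slowing in children who are already short or light; change in z-score should be added.

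*SAP*

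**What the plan says.** Protocol Section 2 lists as a secondary objective of the Treatment Phase: "To evaluate the effect of SOF/VEL FDC on growth and development of pediatric subjects during and after treatment". Protocol Section 3.1 names the matching endpoint: "Growth and development measurements including height and weight percentiles, Tanner Stage, parental height, and bone age". The percentile scale is therefore the protocol's choice, and the SAP carries it out.

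SAP 7.4 sets the derivation: "An age- and sex-specific percentile will be derived for each weight, height and BMI measurement", from the CDC 2000 growth charts. It then sets the summary: "Body weight, height, BMI and percentiles for body weight, height, BMI at each visit, and change from baseline at each visit will be summarized", by age group and "using descriptive statistics (n, mean, SD, median, Q1, Q3, minimum, and maximum"). The section adds "No inferential statistics will be generated" and provides individual data: "A by-subject listing of body weight, weight percentile, height, height percentile, BMI and BMI percentile will be provided".

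Protocol 6.10.5 also asks for raw change: "The difference in body weight and height measurements between Day 1 and End of Treatment", and likewise to posttreatment Weeks 12 and 24.

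Neither document plans a z-score (SD score) for height, weight or BMI. The only z-score in either document is in the bone-mineral-loss row of the toxicity grading scale (Protocol Appendix 3).

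**The concern.** A percentile is a bounded, nonlinear transform of the standardised score. Near the middle of the chart a small shift in standardised height moves many percentile points; near the tails the same shift moves few. Averaging percentile changes over children with different starting points mixes units of different size.

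This matters because the trial has no reference therapy, so the growth chart is the only benchmark for whether children grew as expected. Raw change cannot take its place: children grow over 12 weeks of treatment and 24 weeks of follow-up, so a positive raw change does not exclude slowing. The other growth outputs do not fill the gap. Mid-parental height is only listed (SAP 7.5), bone age is summarised as raw value and raw change (SAP 7.6), and Tanner stage is a shift table (SAP 7.7). The one standardised measure is least sensitive in children who are already short or light, where slowing would be of most interest.

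**Working it through.** The documents state no growth figure, so there is nothing of the plan's to reproduce. The check asks how a fixed loss on the SD scale appears on the planned scale.

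**Inputs.** From SAP 7.4: the scale (age- and sex-specific percentile) and the summary statistics. Assumed, because the documents give neither: the baseline position on the chart and the size of the loss (0.25 SD as the main case, 0.1 to 0.5 SD as the range).

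**Formulas.** Percentile = 100 × Φ(z). A loss d from baseline z changes the percentile by 100 × [Φ(z − d) − Φ(z)]. Compression relative to the median = [Φ(0) − Φ(−d)] / [Φ(z) − Φ(z − d)].

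**Step 1: a loss of 0.25 SD.** At the median, 100 × [Φ(−0.25) − Φ(0)] = 40.13 − 50.00 = −9.87 points.

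| Baseline percentile | z | Percentile after loss | Change (points) | Compression |
|---|---|---|---|---|
| 50th | 0 | 40.13 | −9.87 | 1.0 |
| 25th | −0.67 | 17.76 | −7.24 | 1.4 |
| 10th | −1.28 | 6.28 | −3.72 | 2.7 |
| 5th | −1.645 | 2.91 | −2.09 | 4.7 |
| 3rd | −1.88 | 1.66 | −1.34 | 7.3 |

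On the z scale every row reads −0.25.

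**Step 2: range of losses.** For 0.1 to 0.5 SD, compression is 2.4 to 3.1 at the 10th percentile, 4.2 to 5.6 at the 5th and 6.4 to 9.0 at the 3rd.

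**Step 3: whole-group mean.** If baseline z is N(0,1) and every child loses 0.25 SD, the mean percentile change is −7.0 points. If baseline mean z is −1 with SD 1, it is −5.1. The same uniform loss gives different means depending only on where the group started.

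**Step 4: can the mean have the opposite sign?** Φ is monotone, so each child's sign is preserved, and if every child loses, the mean percentile change is negative. The signs can differ when losses sit low on the chart and gains sit in the middle:

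- Half at z = −2 losing 0.5 SD: 0.62 − 2.28 = −1.65 points (unrounded). Half at z = 0 gaining 0.1 SD: +3.98 points. Mean z change = (−0.5 + 0.1)/2 = −0.20; mean percentile change = (−1.65 + 3.98)/2 ≈ +1.16 points.
- Half at the 5th percentile losing 0.3 SD (−2.41 points) and half at z = 0 gaining 0.1 SD (+3.98): mean z change −0.10; mean percentile change +0.79 points.

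How often this happens when change is unrelated to baseline was simulated with n = 100, baseline mean z of 0 or −0.5, mean change −0.05 to −0.25 SD and SD of change 0.2 to 0.3 (all assumed). A negative mean z change with a positive mean percentile change occurred in 0% to 1.5% of runs.

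**The case against.** The strongest defence is that SAP 7.4 does not rest on the mean percentile change alone. It also gives raw changes, medians, quartiles, ranges and a listing of every child, and a z-score can be recovered from a listed percentile. The summary is descriptive, no decision or test depends on it, and the SAP follows the endpoint that the protocol names. All of this stands, and it makes the point one of scale rather than contradiction or error. It does not supply a group-level standardised amount of growth change: listings give no estimate, and the median and quartiles of percentile change are compressed in the same way as the mean.

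A reader might infer two stronger claims that the documents do not support.

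- *Slowed growth in short children is shrunk sevenfold as a rule.* That factor holds near the 3rd percentile. It is about 2.7 at the 10th and 1.4 at the 25th for the same loss, and the documents do not say how many children start that low. A general slowing would still be visible in the planned mean (Step 3).
- *The planned mean would hide or reverse a real loss.* Reversal requires short children to lose while mid-range children gain, and nothing in the documents points to that pattern. Where it did occur, other planned output would partly show it. In an assumed mixture with half the children near −1.9 SD losing 0.5 SD and half near 0 gaining 0.15 SD (within-half SD 0.3), mean z falls by 0.175 and the mean percentile rises by about 1.7 points. The quartiles of percentile change would be about −2 and +6, with half the children negative.

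**Conclusion.** The concern holds as a weak choice of scale for a secondary-objective measure in a single-arm trial. The mean and SD of percentile change cannot be read as an amount of growth lost, and they understate slowing in children who start low on the chart. The size depends on assumptions the documents cannot settle: for a loss of 0.25 SD, compression runs from about 1.4-fold at the 25th percentile to about 7-fold at the 3rd. A difference in sign between mean percentile change and mean z change is a possibility under a specific pattern, not an expectation. The SAP is consistent with the protocol here, and no stated figure is wrong.

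**What to change.** In SAP 7.4, also derive the age- and sex-specific z-score for each weight, height and BMI from the same CDC calculation (equivalently, the inverse normal of the unrounded percentile). Summarise the z-score and its change from baseline at EOT, FU-12 and FU-24 by age group, using the descriptive statistics already listed there, and add the z-scores to the by-subject listing. Keep the percentiles, since the protocol names them as the endpoint. A descriptive 95% CI for mean z-score change is optional. SAP 6.1.2 already gives confidence intervals for SVR12 while ruling out inferential statistics, so there is a precedent, but the z-score summary answers the point without one.

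The cost is a sentence or two in the SAP and one derived variable per measurement, with no new data, visits or procedures.
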